# Validation of diagnostics to identify glucose-6-phosphate dehydrogenase activity in the US

**NCT04010695**

Short title: US G6PD Validation Study

Version 1.3

Date: 18 March 2019

Principal Investigator:

[name]

Co-Investigators:

Location of Research:

Seattle, Washington

Proposed Project Dates:

March 2019-July 2019

Study title	Validation of a quantitative diagnostic to identify glucose-6-phosphate dehydrogenase activity in the US
Précis	Cross-sectional diagnostic accuracy study with up to 250 patient participants with a goal of obtaining 20 deficient and 20 intermediate samples. The clinic will recruit and consent study participants. Clinic staff will draw 3 EDTA whole blood tubes and obtain finger stick capillary blood. Clinic staff will perform the investigational SD Biosensor point-of-care (POC) test for G6PD deficiency and a HemoCue® hemoglobin test on finger stick capillary blood and on the EDTA anti-coagulated venous blood samples. Another EDTA anti-coagulated venous blood sample will be sent to a CLIA-certified lab for G6PD reference testing by the gold standard assay: G6PD measurement by spectrophotometry; this sample will also have a hemoglobin measurement by a hematology analyzer. Individuals identified as G6PD deficient with the reference test will be notified of their results by the clinic and referred to their physician for follow-up.
Objective	To assess the accuracy of a POC G6PD test as compared to a reference assay in detecting G6PD activity
Endpoints	
 
Sensitivity and specificity of SD Biosensor POC G6PD test compared to the Pointe Scientific test kit for identifying G6PD deficient individuals and women with intermediate G6PD activity
 
Accuracy between the SD Biosensor POC G6PD test measure of G6PD activity and the Pointe Scientific test kit
 
Accuracy between the SD Biosensor POC G6PD test measure of hemoglobin (Hb) and HemoCue 201+, a point of care reference haemoglobin assay
 
Comparison of the SD Biosensor POC G6PD test results for capillary and venous samples.
 

Population	250 male and female participants 18-65 years of age presenting at the clinic for care. Individuals who have received a blood transfusion within the last 3 months, according to self-report, will be excluded.
Study sites	Prevention Center, Fred Hutch Cancer Research Center University of Washington
Study duration	6 months (estimated).

## Abbreviations

CE mark	European Conformity certification
CI	confidence interval
CLIA/CAP	Clinical Laboratory Improvement Amendments/ College of American Pathologists
CLSI	Clinical Laboratory Standards Institute
EDTA	ethylenediaminetetraacetic acid
FDA	Food and Drug Administration
FNTP	false negative true positive
FST	fluorescent spot test
G6PD	glucose-6-phosphate dehydrogenase
G6PDd	glucose-6-phosphate dehydrogenase deficiency
Hb	hemoglobin
IRB	institutional review board
IU	international unit
MTCT	Malaria Clinical Trials Center
POC	point-of-care
PQ	prequalification
P. vivax	Plasmodium vivax
QC	quality control
TPTN	test positive true negative
TTN	test and true negative
TTP	test and true positive
US FDA	United States Food and Drug Administration
UW	University of Washington
WHO	World Health Organization

## 1. Background and rationale for the study

Glucose-6-phosphate dehydrogenase (G6PD) is a critical housekeeping enzyme in red blood cells that supports protective systems against oxidative challenge by producing the reduced form of nicotinamide adenine dinucleotide phosphate [1, 2]. The most common human enzyme defect is G6PD deficiency, which affects more than 400 million people worldwide [3]. This deficiency can be severe, characterized by very low levels of G6PD activity or intermediate, characterized by moderately low levels of G6PD activity. Red blood cells are especially vulnerable to the effects of these mutations because they cannot replenish their supplies of the enzyme once they mature and enter the bloodstream. As a result, these cells are susceptible to hemolysis when subjected to oxidative stress, which can occur after therapy with the anti-malarial 8-aminoquinolines such as primaquine, a few antibiotics, and some anti-inflammatories. Hemolysis can also be activated by other exogenous agents, including foods (e.g., fava beans), henna, and some infections (e.g., hepatitis A or B, pneumonia, and typhoid fever). In newborns, G6PD deficiency is often first manifested as jaundice resulting from hyperbilirubinemia, which, if unchecked, can lead to kernicterus, a form of brain damage.

In 1989, the World Health Organization (WHO) working group on G6PD deficiency recommended that when possible, newborns should be screened for G6PD deficiency where G6PD deficiency is common [4]. However, this screening is not routinely done in the United States [5]. Screening for G6PD deficiency is included in the newborn screening programs of only two states and some facilities outside of those states may choose to adopt universal or targeted screening for G6PD independent of routine newborn screening programs [6,7]. While knowing the G6PD status of a patient is useful clinical information, access to testing for G6PD deficiency is very limited due to the price and complexity of the diagnostic products available for this condition, especially in and low-resource settings.

G6PD status is particularly relevant for the treatment and prevention of malaria. Malaria is prevented and treated using a variety of treatments, some of which pose a high risk to those with G6PD deficiency. The 8-aminoquinoline-based drugs for malaria treatment and prophylaxis, such as primaquine and tafenoquine, are the only ones with the capacity to prevent relapse and eliminate the liver stage parasites in *Plasmodium vivax* infections. Because of the risks associated to G6PD deficiency for primaquine exposure, WHO recommends that “the G6PD status of patients should be used to guide administration of primaquine for preventing relapse” [8].

Currently, the G6PD status of a patient is most often defined by the patient's G6PD phenotype, characterized by analysis of total activity in blood lysate [3]. This method, considered the reference standard, is a costly and complex quantitative laboratory-based spectrophotometric test. The quantitative laboratory test can clearly identify subjects with all ranges of G6PD activities (including those with intermediate levels who may also be at risk of severe hemolysis), but these methods require an equipped laboratory and skilled personnel [9,10]. In field settings, the most commonly performed tests are qualitative devices such as the fluorescent spot test (FST) or the AccessBio, Inc. CareStart™ test [11,12] which can only discriminate gross deficiencies from all the other phenotypes. These are adequate for males who are either deficient or normal in G6PD status. Females, however, who carry two alleles of the G6PD gene, can present as deficient, intermediate, or normal for G6PD activity. Qualitative tests cannot discriminate an intermediate from a normal G6PD status. Quantitative tests are required to provide better case management for women, especially in anticipation of the availability of tafenoquine, which is indicated only for women and men with normal G6PD activity.

Given variety of clinical settings where G6PD status can be used to inform clinical care, point-of-care (POC) G6PD tests are required to support broader availability of primaquine and, in the future, tafenoquine. For treatment of women whose enzymatic activity is estimated to be normal by qualitative testing but is still too low for treatment of high-dose primaquine or tafenoquine, a quantitative portable device will be needed to obtain more accurate levels of G6PD activity to ensure appropriate and safe treatment [13].

PATH and the product developers have assessed the candidate POC test performance through laboratory evaluations using frozen specimens. Next steps in the validation of the POC test include an assessment of diagnostic accuracy using clinical samples in representative use cases.

## 2. Study objectives

The goal of this study is to contribute to a body of evidence that will support the submission of G6PD tests to the US Food and Drug Administration (FDA), WHO prequalification (PQ) process, and for product registration in target countries.

The primary objective is to assess the accuracy of the SD Biosensor STANDARD G6PD Analyzer in measuring G6PD activity when used by trained health care workers. This study aims to establish performance characteristics for SD Biosensor STANDARD G6PD Analyzer when performed from venous and capillary blood samples. Results from the SD Biosensor STANDARD G6PD Analyzer will be compared to results from an FDA-cleared quantitative G6PD assay and FDA-cleared hemoglobin assay: Pointe Scientific test kit.

## 3. Study design

This is a prospective cross-sectional diagnostic accuracy study. Study endpoints include:

- Sensitivity and specificity of SD Biosensor POC G6PD test compared to the Pointe Scientific test kit for identifying G6PD deficient individuals and women with intermediate G6PD activity
- Accuracy between the SD Biosensor POC G6PD test measure of G6PD activity and the Pointe Scientific test kit
- Accuracy between the SD Biosensor POC G6PD test measure of hemoglobin (Hb) and HemoCue 201+, a point of care reference haemoglobin assay
- Comparison of the SD Biosensor POC G6PD test results for capillary and venous samples.

### 3.1 Sample size

The sample size for this study is based on the expected prevalence of G6PD deficiency and on data requirements set by WHO through their process of prequalification of in vitro diagnostics [15]. This requires obtaining samples from participants with a range of G6PD activity levels. The WHO PQ process defines these levels as shown in Table 1.

Table 1. G6PD activity thresholds.

Sex	Level	Threshold	Estimated quantitative thresholds
Female	Deficient	G6PD activity <30% of the adjusted male median	<4 IU/ g Hb
Female	Intermediate	G6PD activity 30% to 80% of the adjusted male median	4-6 IU/ g Hb
Female	Normal	G6PD activity >80% of the adjusted male median	>6 IU/ g Hb
Male	Deficient	G6PD activity <30% of the adjusted male median	<4 IU/ g Hb
Male	Normal	G6PD activity >30% of the adjusted male median	>6 IU/ g Hb

Abbreviation: G6PD, glucose-6-phosphate dehydrogenase.

According to the target product profile, the novel POC G6PD will need to be at least 95% sensitive for detecting G6PD activity levels at 30% to 80% of normal enzyme activity [13]. Sample size calculations for this study are determined by a standard method, sometimes referred to as Buderer's equation, where study sample size requirements are calculated based on a clinically acceptable degree of precision, the hypothesized values of sensitivity and specificity, and the estimated prevalence of disease in the target population [14]. Assuming a sensitivity of 95%, with a confidence interval of 95%, and a 1% to 2% maximum marginal error, a minimum of 162 participants with deficient and intermediate G6PD activity will be needed for the analysis. To account for any possible device/diagnostic failures or compromised blood samples due to insufficient blood, signs of blood degradation, or contamination, the sample size is increased by 20% to approximately 200 participants with deficient activity and 200 participants with intermediate G6PD activity.

In this US, the estimated prevalence of G6PD activity at less than 30% of normal enzyme activity can be up to 12% in certain subpopulations [16,17]. By testing a minimum of 250 individuals, this study aims to include 20 deficient and 20 intermediate individuals.

In order to achieve the target number of deficient and intermediate samples (200), these data will be combined with data generated in other clinical evaluation in the US, Ethiopia and Brazil for regulatory submissions to the US FDA and/or WHO. The additional evaluations will include approximately 3,000 total participants with over 200 expected deficient and intermediate individuals.

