#### 8.1.1 Diagnostic performance

For purposes of diagnostics for G6PD deficiency:

- A true positive: individuals who display  $\leq 30\%$  (threshold) G6PD activity in circulating venous blood as determined by a quantitative assay and in this study specifically the Pointe Scientific Cat No. G7583. (see table 2).
- A true negative: individuals who display  $> 30\%$  (threshold) G6PD activity in circulating venous blood as determined by a quantitative assay and in this study specifically the Pointe Scientific Cat No. G7583. (see table 2).

In order to investigate the performance of the assay to distinguish females with intermediate activity from female with normal activity, the sensitivity and specificity will be determined at G6PD activity thresholds of 70% and 80%. 70% refers to the threshold used in the clinical trials for tafenoquine as a cure to *P. vivax*, and 80% refers to the most recent WHO G6PD phenotype classification.

For the purposes of this study, an individual will be considered G6PD deficient (case) if they test positive by the Pointe Scientific assay. The primary success criterion will be focused on the ability to identify G6PD-deficient patients correctly, such that the SD Biosensor POC G6PD test on fingerstick blood and the Pointe Scientific assay on venous blood should both accurately identify all severely G6PD-deficient specimens (with  $<30\%$  normal) as deficient.

The performance of the POC G6PD test against the Pointe Scientific assay will be determined by calculating the sensitivity and specificity. Sensitivity and specificity of the POC G6PD assay will be calculated as per Domingo et al. [19]. In summary, an adjusted male median will be calculated for both the POC G6PD and Pointe Scientific assay; from this median, the 30%, 70%, and 80% cutoff levels for the two tests will be used to categorically define G6PD-deficient cases.

Sensitivity will be determined using the following method:

- TTP = test and true positive (positive by reference assays according to case definition and positive by the POC G6PD test).
- Fntp = false negative true positive (positive by reference assays according to case definition and negative by the POC G6PD test).
- Sensitivity =  $TTP/(TTP+Fntp)$ .

Specificity will be determined by the following method:

- TPTN = test positive true negative (negative by reference assays according to case definition and positive by POC G6PD test).

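### In Table 1, 4 and 6 IU/g Hb cannot be 30% and 80% of one male median, and men have two IU values for a single 30% boundary

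*Combined protocol and SAP*

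**What the plan says.** Section 3.1, Table 1 defines the activity classes in two parallel columns. The first uses percentages of the adjusted male median. Women are deficient below 30%, intermediate at "G6PD activity 30% to 80% of the adjusted male median", and normal above 80%. Men are deficient below 30% and normal at "G6PD activity >30% of the adjusted male median". The second column, headed "Estimated quantitative thresholds", gives below 4, 4 to 6, and above 6 IU/g Hb for the three female classes, and below 4 and above 6 IU/g Hb for the two male classes. No value of the male median is stated anywhere.

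Other sections use these classes:

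- The précis and Section 3.1 aim for 20 deficient and 20 intermediate participants.
- Section 8.1.3 sets a data stop for the FDA submission once 50 severely deficient, 50 intermediate and 100 normal specimens are available. The data come from studies in Brazil and the US, whose data collection is described in separate protocols.
- Section 5.3 returns G6PD results only to participants who are intermediate or deficient by the reference assay.

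The accuracy analysis works differently. Section 8.1.1 says that "an adjusted male median will be calculated for both the POC G6PD and Pointe Scientific assay", and takes the 30%, 70% and 80% cutoffs from each assay's own median.

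**The concern.** The two columns are presented as the same boundaries in different units. If they are, one median must connect them, and none does. The male rows also disagree within the IU column. Section 1 says of qualitative tests: "These are adequate for males who are either deficient or normal in G6PD status". Table 1's percentage column agrees, with a single boundary, but the IU column leaves a band of 4 to 6 IU/g Hb in which a man is neither deficient nor normal. The same value, above 6 IU/g Hb, stands for more than 80% in women and more than 30% in men.

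What is at stake is who is counted in which class. The 20/20 goal, the data stop and the return of results all use class names while the study is running. The median is something that will be calculated, and the plan does not say when or from whom. The IU column holds the only fixed activity values for these classes in the document. Someone working from that column and someone working from the percentages could class the same specimen differently.

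**Working it through.** **Inputs**, all from Table 1: 30% is paired with 4 IU/g Hb and 80% with 6 IU/g Hb for women. For men, the 30% boundary is paired with 4 on the deficient side and 6 on the normal side. The male median, M, is not given, so the first check uses a ratio that does not depend on it.

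**1. Ratio.** For any M, the 80% cutoff divided by the 30% cutoff is 0.80M / 0.30M = 2.67. Table 1 gives 6/4 = 1.50. If both values were rounded to whole numbers, the largest possible ratio is 6.5/3.5 = 1.86, still short of 2.67. Reading 6 as the 70% cutoff of Section 8.1.1 does not help, because that needs 0.70/0.30 = 2.33. Nor does a separate median for each assay, since each one must give 2.67.

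**2. Implied medians** (IU value divided by percentage).

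| Pairing | Median (IU/g Hb) | Range allowing for rounding |
|---|---|---|
| 4 at 30% | 13.33 | 3.5/0.30 = 11.67 to 4.5/0.30 = 15.0 |
| 6 at 80% | 7.50 | 5.5/0.80 = 6.88 to 6.5/0.80 = 8.13 |
| 6 at 70% | 8.57 | 5.5/0.70 = 7.86 to 6.5/0.70 = 9.29 |

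The first range overlaps neither of the others. Table 1's pair therefore cannot be reproduced. Pairs that would be consistent are 4 and 10.67 (median 13.33) or 2.25 and 6 (median 7.50).

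**3. Size of the mismatch.** At a median of 7.50, 4 IU/g Hb is 4/7.50 = 53%, not 30%. At a median of 13.33, 6 IU/g Hb is 6/13.33 = 45%, not 80%.

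**4. Men.** The single 30% boundary implies a median of 4/0.30 = 13.33 from one row and 6/0.30 = 20.0 from the other.

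**5. What IU counting would do.** The medians 7.50 and 13.33 come from the table. The median of 10 is an assumption for illustration.

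| Median | 30% | 80% | Counted deficient though above 30% | Women intermediate by percentage | Women normal by IU, intermediate by percentage | Men normal by percentage, not by IU |
|---|---|---|---|---|---|---|
| 7.50 | 2.25 | 6.00 | 2.25 to 4 | 2.25 to 6 | none | 2.25 to 6 |
| 10 | 3.00 | 8.00 | 3 to 4 | 3 to 8 | 6 to 8 | 3 to 6 |
| 13.33 | 4.00 | 10.67 | none | 4 to 10.67 | 6 to 10.67 | 4 to 6 |

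Across this range the IU band of 4 to 6 lies inside the percentage band for intermediate women and is narrower than it. So IU counting would over-count deficient specimens (except at 13.33, where the boundaries agree) and under-count intermediate women. Normal women would be over-counted (except at 7.50) and normal men under-counted, so the net normal count has no fixed sign over the range.

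For example, at the assumed median of 10, a specimen at 3.5 IU/g Hb is at 35%: deficient by IU but not by percentage. A woman at 7 IU/g Hb is at 70%: normal by IU, intermediate by percentage.

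**The case against.** The strongest reply is that the IU column does no work. It is labelled as estimated, no procedure applies 4 or 6 IU/g Hb, and the text leans towards percentages. Section 3.1 reasons from "the estimated prevalence of G6PD activity at less than 30% of normal enzyme activity". The success criterion in Section 8.1.1, that both assays "should both accurately identify all severely G6PD-deficient specimens", describes those specimens as below 30% of normal, and Section 8.1.3 uses the same term, severely deficient. The separate protocols may also set the counting rule. All of this stands as a limit on the consequences. It does not repair the table: an estimate may be imprecise, but these two values cannot both come from one median, and no sentence in this document says which column governs the counts.

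Three stronger readings are tempting, and the documents do not support them.

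- A reader might infer that the accuracy results are compromised. They are not, because Section 8.1.1 takes its cutoffs from each assay's calculated median.
- A reader might infer that the data stop would come too early, with fewer than 50 truly deficient specimens. The stop needs all three counts. Over-counting deficient specimens pulls one way; under-counting intermediate women could delay the stop while deficient specimens continue to accrue.
- A reader might infer that the upper limit of intermediate is undefined, because Section 8.1.1 analyses both 70% and 80%. Table 1 sets it at 80%, the target-product-profile sentence in Section 3.1 repeats 30% to 80%, and Section 8.1.1 ties 80% to the WHO classification and 70% to the tafenoquine trials. The 70% figure is an additional analysis cutoff.

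The link to Section 5.3 also rests on the shared class names; that section cites neither Table 1 nor either of its columns.

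**Conclusion.** Table 1 is wrong as written. The ratio is 1.50 where 2.67 is required, rounding reaches only 1.86, and the implied medians of 13.33 and 7.50 IU/g Hb do not overlap even with rounding. Men have two IU values for one boundary and no class between them. This conclusion needs no assumed median.

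The practical effect is conditional. It arises only if someone uses the IU values to count or classify, which the documents neither instruct nor rule out. The directions found above (deficient over-counted, intermediate women under-counted) assume a median between 7.5 and 13.33. The net effect on the data stop is unknown, and the number of specimens affected cannot be computed because the plan gives neither a median nor a distribution of activity. The planned sensitivity and specificity are unaffected. The error should still be corrected, because it sits in the only table that defines the classes and costs little to put right.

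**What to change.** 1. Remove the IU column from Table 1. Alternatively, mark it as indicative and recompute it from one stated reference-assay male median, with a single 30% boundary for men.
2. State in Sections 3.1 and 8.1.3 that recruitment and data-stop counts use the percentage classes already in Table 1, with limits at 30% and 80% of the reference-assay adjusted male median.
3. State which population supplies that median (this study alone, or pooled with the other studies feeding the data stop) and when it is calculated, since counts are needed before the final analysis.
4. Reconcile Table 1 with Section 5.3, so that it is clear what the class names mean when results are returned. This review does not choose a clinical threshold.

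Editorial only: align below 30% in Table 1 with at or below 30% in Section 8.1.1 (a man at exactly 30% falls in neither of Table 1's percentage classes), and change the reference to Table 2 in Section 8.1.1 to Table 1, because Table 2 lists study procedures.

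The cost is a corrected table, a few sentences, and one decision about the source and timing of the median. Enrolment, testing, and the sensitivity and specificity analysis do not change.

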## **5. Study procedures**

### **Recruitment and screening at Seattle Malaria Clinical Trials Center**

Up to 250 adult subjects meeting eligibility criteria will be included in this study. Subjects will be recruited from the greater Seattle area through a variety of Institutional Review Board (IRB)-approved messaging and outreach methods via the MC-002 general screening protocol (IR# 8366). Recruitment methods will target populations with expected

[figure not shown]
high prevalence of G6PD deficiency, including Southeast Asian populations and African-American populations. This will be achieved through outreach with community care facilities in the University of Washington network.

Screening procedures include the informed consent process and obtaining a brief history. The history will include questions regarding ethnicity, age, sex, and current health status. The screening/enrollment visit will take place at the Prevention Center clinic at the Fred Hutch Cancer Research Center. Subjects may be enrolled the same day that the informed consent procedure occurs. Subjects may also be invited to consent to be included in the database maintained for Seattle MCTC activities under the IRB-approved MC-002 general screening protocol and/or in the asymptomatic malaria infection study MC-005. The informed consent will include a provision that the reference laboratory G6PD result for subjects enrolled in MC-005 will be added to the MC-005 study database.

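### The stated sample-size inputs call for at least 457 cases, not 162, and Section 3.1 conflicts on whether the pooled case target is 200 or 400

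*Combined protocol and SAP*

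**What the plan says.** Section 3.1 says that the sample size rests on expected prevalence and on WHO prequalification data requirements. It then names Buderer's equation, cites a target product profile requirement of at least 95% sensitivity for activity between 30% and 80% of normal, and gives the result: "Assuming a sensitivity of 95%, with a confidence interval of 95%, and a 1% to 2% maximum marginal error, a minimum of 162 participants". The sentence describes these as participants with deficient and intermediate activity. A 20% increase for device failures and compromised samples takes the figure to "approximately 200 participants with deficient activity and 200 participants with intermediate G6PD activity".

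The section's closing paragraph explains that the cases will come from pooling with other evaluations: "In order to achieve the target number of deficient and intermediate samples (200"), and "The additional evaluations will include approximately 3,000 total participants with over 200 expected deficient and intermediate individuals". Seattle itself aims for 20 deficient and 20 intermediate participants among 250.

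Section 8.1.1 computes sensitivity at three cutoffs of the adjusted male median: "from this median, the 30%, 70%, and 80% cutoff levels for the two tests will be used to categorically define G6PD-deficient cases". It does not say which of these the calculation in Section 3.1 covers.

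**The concern.** With a true sensitivity of 95% and 162 cases, one standard error is already about 1.7 points. A 95% interval reaching at most 1 to 2 points either side is therefore out of reach, so either the margin or the case number is wrong.

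The section presents this calculation as the statistical reason for its case target. A reader who trusts it expects roughly 93% to 97% around an observed 95%, and precision near 95% matters because the cited requirement is at least 95%.

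The second problem is the unit. If the target is 200 in each category, 400 cases are needed; if it is 200 in all, half as many. Suppose the expected yield of over 200 elsewhere counts both categories together. Adding Seattle's planned 40 then gives somewhat over 240, which passes a target of 200 but falls well short of 400. If the yield is per category, both targets are met. The text does not let the reader tell which applies.

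**Working it through.** **Inputs, all from Section 3.1.** Sensitivity p = 0.95; confidence 95%, taken as two-sided (z = 1.96); margin d = 0.01 to 0.02, taken as the half-width; stated result 162.

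**Step 1: cases required.** n = z² p(1 − p) / d², with z² p(1 − p) = 3.8416 × 0.95 × 0.05 = 0.18248.
- d = 0.02: 0.18248 / 0.0004 = 456.2, so 457 cases.
- d = 0.01: 0.18248 / 0.0001 = 1,824.8, so 1,825 cases.

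The plan's 162 is not reproduced. The ratios are 457/162 = 2.8 and 1,825/162 = 11.3. Prevalence only converts cases to total enrolment (total = cases / prevalence), so it cannot lower the number of cases.

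**Step 2: precision that the planned numbers give.** Half-width = 1.96 × √(0.95 × 0.05 / n).

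| Cases | Half-width (points) | Wald 95% interval | Exact 95% interval |
|---|---|---|---|
| 162 | 3.36 | 91.6% to 98.4% | 90.5% to 97.8% (154/162) |
| 200 | 3.02 | 92.0% to 98.0% | 91.0% to 97.6% (190/200) |
| 400 | 2.14 | 92.9% to 97.1% | 92.4% to 96.9% (380/400) |
| 457 | 2.00 | 93.0% to 97.0% | not computed |

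**Step 3: other routes to 162.**
- One-sided 95% confidence: 322 at d = 2%.
- Two-sided 80% confidence: 196 at d = 2%.
- Continuity correction: 505 at d = 2%.
- Margin as full interval width: 1,825 at d = 2%.
- Margin as a standard error: 119 at 2%, 475 at 1%.
- Finite-population correction with a population of 250 and d = 2%: 456.17 / (1 + 455.17/250) = 161.7, so 162. With d = 1% it gives 220.

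**Step 4: the unit.** 162 × 1.2 = 194.4 and 162 / 0.8 = 202.5. Both are about 200, and the text then assigns 200 to each category. So 162 behaves as a per-category number although it is worded as deficient and intermediate together. The closing paragraph returns to one figure of 200 for both.

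**Step 5: the denominator.** The 400 row needs all 400 to be analysable, although the 20% was added because some will not be, and it needs both categories in one denominator. Under Section 8.1.1 the cases at the 30% cutoff are deficient participants only, so a target of 200 plus 200 supplies at most 200 there. At the 70% cutoff, participants between 70% and 80% are intermediate under Table 1 but are not cases.

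**The case against.** **The gap at the lenient end is smaller.** The margin is called a maximum. If 2 points is acceptable, 457 cases suffice and the shortfall is 2.8-fold; the 11-fold figure applies only if 1 point is required. With 400 cases the half-width is 2.14, which rounds to 2. This stands, but only under the conditions in Step 5, and it does not make 162 the minimum.

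**A hidden assumption may explain 162.** The finite-population correction reproduces it exactly, so a reader might infer that this is its source. The documents do not say so, and it would not justify the figure. The inputs that Section 3.1 lists include no population size, 250 is Seattle's whole enrolment rather than a number of cases, and the pooled data are meant for regulatory use well beyond those 250 people. Likewise, 162 cases have a standard error of 1.71 points, inside the stated range. But the 95% confidence level would then play no part, and neither end of the range gives 162.

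**The inflated target is explicit.** This is correct: 200 deficient and 200 intermediate is clear where it appears. The defect is the conflict with the paragraph that follows, together with the combined wording attached to 162.

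**The cutoff is partly stated.** Section 3.1 links 95% sensitivity to 30% to 80% activity, and no margin is claimed specifically for the 30% cutoff. This stands. It is a reason to name the case group, not evidence that precision promised at 30% has been missed.

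**WHO requirements are a second stated basis.** The 200 may be set by them; the documents do not allow that to be judged. This limits the consequence, but the text attributes 162 to the precision calculation.

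**Conclusion.** The point holds as an error in the stated precision justification. The named method and inputs give 457 cases at 2 points and 1,825 at 1 point, against 162. The planned numbers give about ±3.4 points (162) or ±3.0 (200), and ±2.1 at best (400). Separately, Section 3.1 is inconsistent on whether the pooled target is 200 or 400 cases. The figures assume two-sided 95% confidence, a margin read as a half-width, and the normal approximation at 95% sensitivity.

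A reader might infer that the Seattle study is undersized or that its conclusions are compromised. The documents do not support that. Seattle's 250 is tied to prevalence and an aim of 20 plus 20 cases, and the interim numbers in Section 8.1.3 are set on another basis. No success criterion in Sections 8.1.1 and 8.1.2 uses the 1% to 2% margin. Nor do the documents show that the pooled programme will miss its target, because the unit of the expected yield is not stated. This should be fixed, but at the level of wording unless the margin is a real requirement.

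**What to change.** 1. Replace the 1% to 2% margin with the precision that the planned numbers give at 95% sensitivity: about ±3.4 points for 162 analysable cases, about ±3.0 for 200. Show the formula.
2. State that 162 and 200 are per category, or combined if that is meant. Align the closing paragraph of Section 3.1, including the unit of the expected yield of over 200.
3. Say which case group or which of the 30%, 70% and 80% cutoffs the calculation covers.
4. If WHO requirements actually set the 200, say so and present the precision as a consequence.

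The cost is protocol wording and a less favourable stated precision.

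If the 1% to 2% margin is truly required, the number must change instead: 457 to 1,825 analysable cases for each group sized, or 549 to 2,190 with the protocol's 20% added (457 × 1.2 = 548.4; 1,825 × 1.2 = 2,190). If both categories are sized separately, the totals double to 914 to 3,650, or 1,098 to 4,380 with the 20%. That would be a substantial enlargement of the pooled programme.
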